Methodology Overview	
Once IRB approval has been obtained, the sponsor team, [name] (University of Massachusetts) and Dr. [name] will begin training Research Coordinators at two study sites: Tufts Medical Center and Eskenazi Hospital. Research Coordinators will establish data collection methods (Case Report Forms) in REDCap (an online database for research data and surveys) at each site, RF MAC Systems will be shipped to the sites, charged and prepared for assignment to patients as they are enrolled in the study at their final pre-operative appointment. Each site will enroll 150 patients (300 patients total) and patients will be randomized in to one of two groups: Control (Group 1) or Intervention (Group 2). Participants will receive an identification number and all data collected will be password-protected. The study consists of two parts: in-patient and at-home. All participants will participate in both parts of the study.
 
In-Patient:
 
 
1. In the pre-operative appointment, the Research Coordinator will enroll participants and they will be randomly assigned to a study Group (control or intervention) and baseline information will be collected on the CRF.
 
2. A 4-meter walk test will be performed and the Research Coordinator will enter results in the patients CRF.
 
3. On the day of surgery, the patient will receive standard of care for each site for patients undergoing a THR or TKA. Patients in the control group (Group 1) will receive the site's standard of care IPC for DVT prophylaxis. Group 2 (intervention) will receive the RF MAC System for DVT prophylaxis. In addition, patients in both groups will receive an activity tracker.
 
4. In the first 24 hours post-operative, the Research Coordinator will visit the patient's room for observation a total of two times. During these visits, the Research Coordinator will visually observe the status of the DVT prevention device (control or intervention) to determine if it is properly applied to the patient's lower extremities and fully operational. This information will be recorded in REDCap. For Group 1 (control), this information will be collected by via observation by the Research Coordinator and patient interview. For the MAC System Group 2, this information will be collected automatically by the device and recorded by the Research Coordinator during the periodic visits.
 

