## **4. STUDY OVERVIEW**

### **2.4 Study Approach**

Once IRB approval has been obtained, the RF study team will begin working with site Research Coordinators to implement the study. The initial phase will focus on planning and training, followed by enrollment of initial patients.

Once patient enrollment begins, each site will recruit a total of 150 patients (75 in control group and 75 in intervention group). Inclusion criteria includes adult patients (age 40-85) who are having their first elective total hip replacement (THR) or first or second (opposite knee) elective total knee replacement (TKA), speak English and are expected a hospital stay of two days or less with plans to discharge to home from hospital (not a rehabilitation facility). In addition, participants must be able to perform self-care, have a BMI between 18 and 39 and a calf circumference between 11 and 24.5 inches.

Exclusion criteria includes patients scheduled for a partial joint replacement, TJR revisions, emergency surgeries, those with calf deformities that would not allow proper fit for external compression devices, or patients who are non-ambulatory, clinically malnourished or frail/deconditioned. Finally, vulnerable patients (pregnant women, prisoners, homeless and cognitively impaired) and those that do not speak English are excluded from this study. Product labeling and materials are currently only available in English.

Table 1: Clinical Study Plan				
Site	Eskenazi Hospital		Tufts Medical Center	
Principal [name]		[name], MD & [name], MD	
Group (1 is Control; 2 is Intervention)	1	2	1	2
Targeted Enrollment	75	75	75	75
Total Targeted Enrollment per Site	150		150	
Total Projected Study Enrollment	300			

Each site will record the total number of patients screened, the number of patients excluded and the reason for the exclusion. These screening statistics will be reported to the Sponsor at the conclusion of the study.

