## **2.5 Study Duration**

The total duration of the study is expected to be 18 months (site training, recruitment, enrollment, participation, case closeout, analysis, completion of final report). This study will include two groups. Group 1 will serve as the control group and will receive standard care. Group 2 is the intervention group and will receive standard care and the proposed intervention, the RF MAC System. Group 1 will consist of 75 patients at each of two sites (total of 150 patients). Group 2 will consist of 75 patients at each of two sites (total of 150 patients). Patients will be assigned to a group by a site Research Coordinator using a random numbers generator at their final pre-operative appointment.

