# **3 STUDY POPULATION**

## **3.1 Sample Size and Target Study Population**

The following vulnerable patients will be excluded from the study: pregnant women, prisoners, homeless and cognitively impaired. Data will be collected at two locations, one site for each cohort.

Each of the two study sites are responsible for recruiting participants in the study (150 total participants, with 75 in each of two study groups).

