## 7 STATISTICAL METHODS

### 7.1 Determination of Sample Size and Planned Analyses

[name] (University of Massachusetts) is responsible for statistical design and power on this study. First, the team will test the group differences on demographic profiles and between RF1400 (Group 2) and standard-of-care (Group 1). If unbalances on any of these characteristics exist, the Horvitz-Thompson weights or propensity scores will also be adjusted to adjust for bias (d'Agostino, 1998). [name] will also compare the characteristics of the individuals who will drop out of the study with those who complete the study and create weights to adjust for any potential bias. For study, Recovery Force hypothesizes that the in-hospital outcomes measures (minutes of use in the first 24 postoperative hours, number of steps in the first 24 postoperative hours and the amount of

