time required by acute care nursing staff to get the patient ready to ambulate) for the patients in RF1400 group (Group 2) will significantly outperform those in standard IPC prophylaxis group (Group 1). Similarly for the Aim 2 at-home outcome measures, (minutes of use per day in the first 14 days of at home use and gait speed at 14 days using the 4-meter walk test, Recovery Force hypothesizes that patients in RF1400 group (Group 2) will significantly outperform those in standard of care group (Group 1). All outcomes are continuously measured. To test Aim 2, let  $E_1$  be the indicator variable of group 1 ( $E_1=1$ ) vs. group 2 ( $E_1=0$ ), and  $Y$  stands for the outcome variable,  $Z$  refers to other relevant background and/or clinical variables (age, gender, comorbidities, etc.), the analysis of covariance (ANCOVA) model will be used to assess the difference between groups, i.e., and the team will have  $Y = \beta_0 + \beta_1 E_1 + \beta_2 Z + \varepsilon$ , estimated to give corresponding  $b$  parameters for  $\beta$  by ordinary regression. The significance of coefficient of  $\beta_1$  will be tested to show the group differences. The interaction term of treatment indicator and center indicators will also be tested to examine the homogenous treatment effect across the two study sites. The study was powered assuming 80% of power and 0.05 significance level; the study will require 130 patients per group to detect a medium effect size (EF) of 0.35 difference between groups for a continuously measured outcome. Assuming up to a 15% dropout, each site will enroll 150 patients in each group. The graph below shows the different sample size requirements to detect a certain EF at power of 0.8 or 0.9.

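### Section 7.1 as written enrols 600 patients (150 per group at each of two sites), twice the 300 given in the rest of the protocol

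*Combined protocol and SAP*

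**What the plan says.** Section 7.1 sets power at 80% and significance at 0.05, and states that "the study will require 130 patients per group to detect a medium effect size (EF) of 0.35 difference between groups". It then converts this to enrolment: "Assuming up to a 15% dropout, each site will enroll 150 patients in each group".

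The other enrolment statements are:

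- **Synopsis, objectives, and section 2.2:** 300 patients.
- **Synopsis, planned number of subjects:** 75 per group at each of two sites, 150 per group.
- **Synopsis, methodology overview:** "Each site will enroll 150 patients (300 patients total").
- **Section 2.4:** "each site will recruit a total of 150 patients (75 in control group and 75 in intervention group"). Table 1 in the same section shows 75 in each group-by-site cell, 150 per site and 300 overall.
- **Section 2.5:** "Group 1 will consist of 75 patients at each of two sites (total of 150 patients"), and the same for Group 2.
- **Section 3.1:** "150 total participants, with 75 in each of two study groups", which is a per-site figure on the natural reading, since the sentence is about what each site must recruit.

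Section 3.1 also says: "Data will be collected at two locations, one site for each cohort".

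**The concern.** Section 7.1 and the rest of the protocol differ by a factor of two on total enrolment. No single other section states every figure (per cell, per group and total), but they agree with one another, and section 7.1 agrees with none of them.

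The location matters because section 7.1 is the only place that gives power, significance level, effect size and dropout together. An ethics board, the funder or a reader of the results would go there to check the justification for the number of patients. As the sentence stands, that check fails, and a completed 300-patient trial could be read as having stopped at half its target.

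Two smaller points belong to the same edit. The dropout allowance does not quite deliver the stated 130 evaluable patients per group. And the section 3.1 wording about one site per cohort, if cohort means treatment group, would put each group at a different site.

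**Working it through.** **Inputs.** From section 7.1: effect size 0.35 SD, power 80%, significance level 0.05, 130 evaluable per group, dropout up to 15%. Two sites and two groups from section 2.4, Table 1. Section 7.1 does not say whether the test is one- or two-sided. I assume two-sided, because that reproduces the stated 130; a one-sided test gives about 101 per group.

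**Step 1: reproduce the plan's figure.** The normal approximation is n = 2(1.960 + 0.842)² / 0.35² = 128.1, so 129 per group. The two-sample t-test gives 129.1, so 130 per group. The stated 130 is correct.

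**Step 2: total enrolment.**
- Section 7.1 as written: 150 × 2 groups × 2 sites = 600.
- Elsewhere: 75 × 2 groups × 2 sites = 300.

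**Step 3: which total fits the inputs?**
- 130 × 1.15 = 149.5, which rounds to 150 per group.
- At 600 patients there are 300 per group. After 15% dropout 300 × 0.85 = 255 remain, and power for 0.35 SD is 97.6%, not 80%.
- Going from 300 enrolled to 130 evaluable per group would need dropout of 1 − 130/300 = 56.7%, not 15%.

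Only 150 per group across both sites is compatible with the stated inputs.

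**Step 4: the dropout allowance with 300 patients.** To keep 130 after 15% dropout, the formula is n / (1 − d): 130 / 0.85 = 152.9, so 153 per group. The figure of 150 matches n × (1 + d) instead. With 150 enrolled, 150 × 0.85 = 127.5 remain. The dropout that leaves exactly 130 is 1 − 130/150 = 13.3%.

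| Dropout | Evaluable per group | Power for 0.35 SD (unadjusted t-test) |
|---|---|---|
| 0% | 150 | 85.6% |
| 5% | 142.5 | 83.8% |
| 10% | 135 | 81.7% |
| 13.3% | 130 | 80.3% |
| 15% | 127.5 | 79.5% |

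The effect detectable with 80% power is 0.349 SD at 130 per group and 0.352 SD at 127.5.

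**Step 5: the section 3.1 wording.** One site per cohort cannot be squared with the sentence that follows it (75 in each of two groups at each site), with Table 1, or with the treatment-by-center interaction test planned in section 7.1, which needs both groups at both sites.

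**The case against.** The strongest reply is that this is editorial. The total of 300 is explicit in the synopsis, section 2.2 and Table 1, the inputs in section 7.1 cannot yield 300 per group, and nothing else in the plan uses 600. All of that is true. It settles what was meant, but it does not correct the sentence, which gives a wrong figure in the governing statement on sample size.

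The dropout point can fairly be called immaterial:

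- The 15% is a ceiling, and the shortfall there is 2.5 patients per group, or 0.8 points of power.
- The plan gives no inflation formula, so n × (1 + d) is an inference from the match to 149.5.
- The 79.5% is for an unadjusted comparison, whereas section 7.1 plans ANCOVA. If covariates explained 2% of the outcome variance (an assumption), power at 127.5 per group would be 80.3%; at 5% it would be 81.5%, and at 10% it would be 83.5%. The weighting that section 7.1 also allows could pull the other way.

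These arguments stand, and the point is kept only as a minor note.

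How far losses after discharge matter depends partly on wording. Hypotheses 2 and 4 rest on in-hospital measurements; section 7.1 lists, for example, "number of steps in the first 24 postoperative hours". Hypothesis 1 is in-hospital in the synopsis, but section 2.2 drops that limit and section 7.1 also names minutes of use at home over 14 days. On the synopsis wording, only gait speed at day 14 among the four primary hypotheses is exposed to losses after discharge; on the section 2.2 wording, adherence may be too.

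Finally, cohort is not defined, so reading it as treatment group is an interpretation. The wording is a separate, minor matter and adds no weight to the discrepancy of 600 against 300.

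**Conclusion.** The concern holds. Section 7.1 states 600 patients by its literal wording, against 300 in the rest of the protocol, and the documents do not reconcile them. The plan's own numbers point to a drafting slip for 150 per group across both sites. This should be fixed because of where it stands, not because the design is at risk.

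On the 300-patient design there is no material underpowering: at the full 15% dropout, power is 79.5% instead of 80.3%. These figures assume a two-sided, unadjusted two-sample t-test at 0.05 with a standardised difference of 0.35. The sample-size graph mentioned in section 7.1 was not available and was not used.

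**What to change.** Replace the last enrolment sentence in section 7.1 with a statement that the study will enrol 150 patients per group, 75 per group at each of two sites, 300 in total. Then give one of two consistent consequences: this allows about 13% dropout while keeping 130 evaluable per group, or it gives about 79.5% power for 0.35 SD at 15% dropout. If the second is used, say that the figure is for an unadjusted comparison. State also that the test is two-sided, if that is what was intended.

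In section 3.1, replace the wording about one site per cohort with a statement that both groups are enrolled at each site.

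The cost is wording only, with no extra patients. What changes is the stated dropout allowance (from 15% to about 13%) or the stated power (from 80% to about 79.5%). Raising enrolment to 153 per group is not warranted by a shortfall of this size.

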## 7.2 Bias Minimization

All subjects meeting the specified eligibility criteria will be enrolled using a convenience sampling strategy.

# 8 ADVERSE EVENT REPORTING

## 8.1 Non-Device-Associated Adverse Events

Adverse events occurring during the enrollment period should be documented by the Investigator in progress notes but will not be collected or analyzed by Recovery Force unless considered serious.

Serious adverse events (SAEs) encountered during study enrollment will be documented by the Investigator and reported to Recovery Force immediately upon discovery. SAEs are defined under current Good Clinical Practice (cGCP) guidelines as events that result in one or more of the following:

- life-threatening illness or injury;
- permanent impairment of a body structure or a body function;
- medically necessary in-patient hospitalization;
- medical or surgical intervention necessary to prevent permanent impairment to body structure or function; or
- fetal distress, fetal death, or congenital abnormality.

SAEs will be reported using an Unanticipated Adverse Device Effects (UADE) form which serves the dual role of capturing pertinent SAE information per industry guidelines and capturing device

information pertinent to medical device standards. Other serious events that affect the rights, safety, or welfare of subjects must also be documented on the UADE form and must be reported immediately to Recovery Force and to the Investigator's IRB according to that IRB's policies.

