### **2.3 Secondary**

Measure patient reported outcomes (PRO) of comfort, device acceptance and ease of use and measure nurse perceptions of device acceptance and ease of use and collect feedback from nurses and physical therapists.

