Once the walk test is complete, the Research Coordinator will direct the patient to complete a final survey. Next, the patients will return all study equipment (activity tracker and the RF MAC System) to the Research Coordinator. Patients who return all equipment will receive their \$100 remuneration for study participation. Renumeration will be reduced by 50% to \$50.00 for any patients who do not return their equipment. Patients who did not return the devices will receive a postage-paid package for returning both the activity tracker and RF MAC device to Recovery Force. Once the equipment has been received by Recovery Force, the additional \$50 remuneration will be mailed to the participant. In addition, participants at Tufts Medical Center will receive \$21 stipend as reimbursement for parking costs.

Research Coordinators will also send at-home physical therapists of individuals in Group 2 a link to a brief survey about the RF MAC.

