#### **4.1.2 RF Movement and Compressions (MAC) Device Safety and Handling Issues**

The Recovery Force MAC System consists of three components: the strap, designed for single patient use; and the controller, designed for multi-use, and the charging hub. If you are, or may be, pregnant, do not use. Recharge battery using an outlet readily accessible for quick disconnect. Do not use where aerosol (spray) products are being used or oxygen is being administered.

Electromedical devices have the potential for explosion in these situations. Never use pins or other metallic fasteners with this product as these could damage the wiring of the device. Care must be taken when operating this equipment around other equipment to avoid reciprocal interference.

Potential electromagnetic or other interference could occur to this or to the other equipment. Try to minimize this interference by not using other equipment in conjunction with this device. Keep and store when not in use out of reach of children, pets, pests, and away from water. No modification of this equipment is allowed. No user serviceable parts inside. If you experience pain, swelling, sensation changes, discomfort or any unusual reactions (including allergic reactions to the materials in this device) while using the device, stop using the device and consult your physician immediately. If pulsing or throbbing occur, the device may be wrapped too tightly. Loosen immediately. This device should not be used adjacent to or stacked upon other devices.

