## **8.2 Device-Associated Adverse Events**

### **8.2.1 Definition of an unanticipated adverse device effect (UADE) event**

A UADE event, as defined by cGCP guidelines, is any SAE, life-threatening problem, or death caused by or associated with a device (or with the process of evaluating a device) if that SAE, problem, or death was not previously identified in nature, severity, or degree of incidence in the investigational plan or application (including a supplementary plan or application), or any other unanticipated, serious, device-associated problem that relates to the rights, safety, or welfare of subjects or operators using the investigational product system or the comparator product system.

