### **8.2.2 Reporting of device-associated adverse events**

The Investigator will be responsible for reporting any UADEs to Recovery Force and to the Investigator's reviewing IRB. UADEs will be documented by the Sponsor on UADE forms.

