# **9 RISK ANALYSIS**

## **9.1 Potential Risks of the Investigational Product and Clinical Investigation**

All subjects will be entering the study voluntarily and the nature of this study should involve minimal risk for study subjects. The only anticipated risks include the possibility of discomfort with the use of the RF MAC Device and potential for feeling uncomfortable with legs exposed during the data collection process. There is also potential for lack of patient satisfaction with the device.

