## **9.3 Minimization of Risks**

Patients who experience discomfort with the device can discontinue use immediately to avoid further discomfort.

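### In the protocol body, non-serious reactions for which section 4.1.2 says to stop the device have no stated collection by group

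*Combined protocol and SAP*

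**What the plan says.** Section 4.1.2 lists what should make a user stop: "If you experience pain, swelling, sensation changes, discomfort or any unusual reactions (including allergic reactions to the materials in this device". The sentence ends by telling the user to stop and see a physician at once. It does not ask for a report to the study.

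Section 8 divides events in two. Section 8.1, headed as non-device-associated, says that adverse events "should be documented by the Investigator in progress notes but will not be collected or analyzed by Recovery Force unless considered serious". Section 8.2 deals with device-associated events, but only as UADEs. Section 8.2.1 defines these as "any SAE, life-threatening problem, or death caused by or associated with a device" that the plan had not already identified, or another serious, unanticipated device problem. Under 8.2.2 the investigator "will be responsible for reporting any UADEs to Recovery Force" and to the IRB.

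Section 9.1 describes the study as minimal risk: "The only anticipated risks include the possibility of discomfort with the use of the RF MAC Device", together with unease at having the legs exposed. Section 9.3 adds: "Patients who experience discomfort with the device can discontinue use immediately to avoid further discomfort".

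The nearest planned data are the secondary aims in section 2.3: "Measure patient reported outcomes (PRO) of comfort, device acceptance and ease of use". In section 2.4, under At Home, "the Research Coordinator will direct the patient to complete a final survey" at the two-week visit, and this is not limited to Group 2. Surveys of the care team and the home physical therapist are also planned. The body does not list the questions in any of them.

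**The concern.** The RF MAC is described as novel (section 2.1), and Group 2 patients take it home. The protocol warns of five kinds of reaction serious enough to stop using it, yet the only stated rule for non-serious events is that the sponsor will not collect them. A rash under a strap, or numbness that settles when the strap comes off, would rarely count as serious. It is still what a prescriber would want to know about a wearable device.

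The trial's conclusions on adherence, steps, gait speed and preparation time are not at stake. What may be lost is a simple tolerability table: how many patients in each group had each reaction, and how many stopped the device for it. Without it, the minimal-risk statement in section 9.1 cannot be checked against the reactions the protocol itself names. Low minutes of use caused by a skin reaction would also look the same as low minutes caused by lack of interest.

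**Working it through.** **Step 1: each reaction in 4.1.2 against the rest of the body.**

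| Reaction | Named in 9.1 or 9.3 | Named as an outcome | Sponsor collection if non-serious |
|---|---|---|---|
| Discomfort | Yes | Comfort (2.3) | Through the comfort outcome |
| Pain | No | No | None stated |
| Swelling | No | No | None stated |
| Sensation change | No | No | None stated |
| Unusual or allergic reaction | No | No | None stated |

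Discomfort is covered. The other four are not.

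**Step 2: does section 8 catch them?** Read by its heading, 8.1 does not apply to a device reaction, and 8.2 applies only if the event is serious. Read as covering all adverse events, 8.1 applies and says that non-serious events are not collected. The result is the same either way.

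**Step 3: other routes in the body.**
- Calls (2.4, At Home): compliance reminders and a chance to ask questions; no symptom query is stated.
- Minutes of use (2.4): would fall if a patient stopped, but no field for the reason is listed.
- Planned analyses (7.1): use, steps, preparation time and gait speed; no tolerability outcome.
- Surveys: content not given in the body.

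**Step 4: what a count could show.** The plan has no figure to reproduce and gives no event rates, so the rates below are assumptions. Group size is 150 (2.5); 130 is the number required per group in 7.1.

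Allergic or sensory reactions in Group 2:
- Upper one-sided 95% bound with zero events: 1 − 0.05^(1/n). For n = 150 this is 1.98%; for n = 130, 2.28%.
- Expected patients at an assumed 1% to 5%: 150 × 0.01 = 1.5 to 150 × 0.05 = 7.5.
- Chance of at least one: 1 − 0.99^150 = 77.9% to 1 − 0.95^150 = 99.95%.

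Pain and swelling also arise from surgery, so the zero-event bound does not apply. The Newcombe 95% interval for a group difference, with equal observed rates, has these half-widths:

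| Assumed rate in both groups | 150 per group | 130 per group |
|---|---|---|
| 10% | ±7.0 points | ±7.5 points |
| 50% | ±11.2 points | ±12.0 points |

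A pain or swelling comparison would be descriptive only.

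**Step 5: cost of asking.** Planned contacts: 2 in-patient visits + (2 calls × 2 weeks) + 1 two-week visit = 7. Checklists: 300 × 7 = 2,100. At an assumed 1 minute each, 2,100/60 = 35 hours; at 3 minutes, 6,300/60 = 105 hours.

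**The case against.** The sponsor can say that this is a deliberate and openly stated choice. The aims are adherence and mobility, no safety endpoint is promised, and section 11.1 claims exemption from the IDE regulations. Section 4.1.2 reads as user labelling rather than a list of expected trial events. All of this stands, and it is why the point is minor.

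A reader might infer that these reactions go unrecorded. The documents do not support that. Section 4.1.2 sends the patient to a physician, section 3.2 recruits from the investigators' own clinics, section 8.1 asks for a progress note, and section 10.3 gives the sponsor access to source documents. What is missing is a count obtained in the same way in both groups. Unsolicited notes cannot later be turned into one.

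A reader might also infer that the trial has no tolerability items at all. That cannot be concluded either. The patient, care-team and therapist surveys are broad enough to hold such questions, and the survey forms, CRF and site appendices were not seen. The finding is limited to what the body states.

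The objection that pain and swelling results would be imprecise is also correct. Whether pain is unexpected after joint replacement is a subjective judgement, made with the device in view. This limits what those two rows can show, but applies less to skin, allergic and sensory reactions.

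**Conclusion.** The point holds for the protocol body, as a minor one. Four of the five reactions in 4.1.2 have no stated by-group collection when non-serious, and no stated record of the device being stopped because of them. The conclusion assumes that the unseen forms do not already ask. No hypothesis, sample size or planned test is affected. The rates in the working are assumptions that show what a count could be worth; the finding does not depend on them.

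Two further inferences are not supported. One is that device is compared with device only until discharge: sections 2.4 and the synopsis allow Group 1 standard IPC at home, so for some patients that comparison may continue. The other is that the silence of 9.1 and 9.3 changes what counts as a UADE: section 4.1.2 is itself part of the plan, and a UADE must be serious, whereas this point concerns non-serious events.

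**What to change.** Amend section 8 so that non-serious reactions listed in 4.1.2 are collected, and add one short REDCap checklist:
- sensation change;
- skin or allergic reaction;
- pain or swelling under the device that the patient or staff find unexpected;
- other;
- for each: date, leg, whether a device was in use, and whether it was stopped for this reason.

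Ask it in the same words in both groups at the existing in-patient visits, calls and two-week visit. Report the number of patients with each reaction, and the number who stopped, by group and descriptively. Separate the in-hospital and at-home periods, and show which Group 1 patients had a compression device at home. Leave the minutes of use for Hypothesis 1 unadjusted.

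If the unseen forms already contain these items, a cross-reference in section 8 and the by-group table are enough.

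Cost: one form, one table, a wording change, no extra contacts, and the 35 to 105 coordinator hours worked out above. Investigator time to review positive answers comes on top. If pain were flagged by an assumed 10% to 50% of patients, that is 300 × 0.10 = 30 to 300 × 0.50 = 150 patients to review, and likewise for swelling. Limiting the question to unexpected pain or swelling should keep the number down.
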